The DMC will be responsible for review of the SAEs and AEs for each site and across the study as a whole. The DMC will make all decisions for stopping the study based on safety concerns, should any present. Early analyses before the study is completed may result in stopping of the study. For example, if it is statistically demonstrated that the results for either efficacy or futility to date could not be changed with further enrollment, the study may be stopped. When repeated significance tests are performed on accumulating data as part of a routine monitoring function, the overall type-I error rate is inflated and the probability of a false positive finding is also increased. A number of methods have been developed to provide guidance on study termination rules based on multiple looks at the primary outcome measures for the review committees while keeping the overall type-I error rate maintained at 5%. For this study, the O'Brien-Fleming method for alpha spending and rejection/acceptance boundaries will be suggested for Type-I error rate control (see Statistical Analysis Plan (SAP – Section XIII) for further details) but the DMC will make the final decision on the type of stopping rule that will be used for the study.

XII. QUALITY ASSURANCE PROCEDURES

Centralized and on-site reviews and monitoring of clinical site practices will be conducted at several levels. The National Coordinator will visit each site two times per year during the enrollment years to monitor the EAW Training, patient safety, and compliance with the study protocol. The Co-National Coordinator will visit each site one time annually during the enrollment years to monitor standardization of the QOL assessments and protocol compliance. Participant's medical records will be made available to the CSP Site visitors as a requirement for participation in this study.

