Sample size/power calculation for the Primary Outcome (2) SCI-QOL for Bladder, Bowel and Pain: An improvement of 10% in the sum T-score of the patient-reported outcomes from the combined SCI-QOL item banks for bladder management difficulties, bowel management difficulties and pain interference is clinically significant. As such, it is hypothesized that 42% of the Intervention group compared with 10% of the Control group will demonstrate a clinically significant change of 10% improvement from baseline to the end of the intervention phase on the sum T-score in the combined SCI-QOL item banks for bladder management difficulties, bowel management difficulties and pain interference. (Table 7).

Sample size/power calculation for the Major Secondary Outcome for Total Body Fat Mass: Patients with a new SCI can be expected to gain an average of 6.0 ± 8.9 kg of fat mass in the first 14 months after injury (manuscript in preparation from our Center). This gain in fat mass appears to continue throughout the duration of their life after SCI. As demonstrated in the preliminary data, an intervention that supports a 1.0 kg (2.2 lb.) loss of fat mass is a substantial amount of fat mass to lose in three months for a person with SCI. Very few interventions have demonstrated changes in body composition of this magnitude in the SCI population. It is expected that 35% of the Intervention group compared with 10% of the Control group will maintain total body fat mass loss during the home/community use phase of the intervention.

Assuming the proportion in the control group achieving a clinically meaningful change to be 10% (or 0.100) for all three outcome measures, and estimating the attrition rate at 15%, the sample sizes range from a low of 71 per group (95% power) for the SCI-QOL PMH outcome to a high of 79 per group (80% power) for the MCS/VR-36 group. As a note about Table 7, to adjust for multiple outcome measures, a significance level of 0.025 was used in the sample size calculations for the co-primaries (MCS/VR-36 and SCI-QOL) and also for the major secondary outcome measure (Total Body Fat Mass). Based on the sample size and power calculations in Table 7, the study will enroll a total sample size of 160 participants, 80 per group.

Table 7: Sample Size/Power Calculations			
Two group continuity corrected χ^2 test of equal proportions (odds ratio = 1) (equal n's)	MCS/VR-36	SCI-QOL (PMH)	Total Body Fat Mass
Test significance level, α	0.025	0.025	0.025

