group will have a clinically meaningful change in the outcome measures for sample size/power calculations. Ten percent is thought to be a conservative estimate as there is no reason to expect the control group to have clinically meaningful changes in quality of life measures or in total body fat mass while continuing to receive SOC for their spinal cord injury. However, as a means of verifying the control proportion of 10% (or 0.100), the proportion of participants considered successful in the control group for all three outcomes and 95% confidence intervals for the proportions will be reviewed upon the completion of the feasibility phase. Based on the extensive experience with this population it is highly unlikely that the assumed success rates in the control group (SOC) will be any higher than the assumed 10%.

At the completion of the feasibility phase, the study will be moved to a continuation phase where the remaining sites (9 remaining sites) will be activated and the remaining participants will be recruited.

D. Baseline Comparability

Baseline comparability between the treatment groups will be evaluated with respect to such variables as demographics (e.g., age, gender, and race) and baseline values of outcome measures (MCS/VR-36, SCI-QOL, total body fat mass, etc.). Chi-square and analysis of variance techniques, as appropriate, will be used to determine any differences in distribution of the variables across the treatment groups. Any variable that appears to be different between the groups ($p < 0.10$) will be considered as a potential covariate in statistical analyses.

E. General Outcome Analysis Guidelines

All statistical tests will be 2-sided. The two primary and major secondary outcome measures will be tested at a 0.025 level of significance. Because of the large number of secondary outcomes to be analyzed, all other secondary outcomes will be tested at a significance level of 0.01 to maintain control over Type I error. SAS 9.4 will be used to conduct all the statistical analyses. A variety of analytic methods will be used for the primary endpoints, secondary endpoints and other analyses.

F. Analysis of Primary and Major Secondary Outcome Measures

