The primary analysis will be based on an intent-to-treat (ITT) model. All participants who are randomized will be included for both groups, whether they are study completers (participants who complete the study through the four-month intervention phase) or early terminators (drop-outs). In order to test the hypotheses for the primary and major secondary outcome measures, each randomized participant will be deemed a success or failure at attaining: 1) ≥ 4.0 point improvement in the MCS of the VR-36, 2) $\geq 10\%$ improvement in the SCI-QOL bladder management difficulties, bowel management difficulties and pain interference sum T score, and

3) ≥ 1 kg. total body fat mass loss. For each of the outcomes, the proportion of participants successful at achieving a clinically significant improvement will be compared between the two groups (Intervention vs. Control) using a chi-square analysis. These will constitute the primary and major secondary efficacy analyses. Participants who drop out will be treated as failures. As such, by design, there will be no missing data: participants either meet the outcome criteria (successes), do not meet these criteria (failures) or they drop out (also failures).

G. Secondary Analyses

In addition to the primary analysis, several secondary analyses will be performed and are described below.

1. Analyses will be performed that include only those participants who complete the study (excluding drop-outs):
 - a) Chi-square analyses of the primary and major secondary outcome measures (proportion of successes) will be repeated for only those participants who complete the 4-month intervention phase.
 - b) Analyses of the MCS/VR-36, SCI-QOL, total body fat mass loss, Global Impression of Change and other secondary outcome measures will include comparisons of the mean difference scores (change from baseline to the end of the intervention phase) of these outcome variables using t-tests.

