For the DMC to make its recommendation for continuation of the study, it will be necessary for them to see the analysis of the primary and major secondary outcome measures every time they are provided a report of study progress and it is possible to calculate these measures. Periodic monitoring of interim results can significantly affect the probability of making an incorrect decision (Type-I error rate). One interim look at the primary outcome measures (in addition to the final “look” at study’s end) will be proposed to the DMC for making the recommendation about whether or not to continue the trial or to stop for early efficacy. It is proposed that the one look occur when 80 (50%) patients have completed participation in the study. The O’Brien-Fleming method for alpha spending and rejection/acceptance boundaries will be suggested for Type-I error rate control. The O’Brien-Fleming boundaries for rejection (α) and acceptance (β) as well as the Type-I error rates for the two looks are given in Tables 15 and 16 for the MCS/VR-36 and SCI-QOL/PMH outcomes, respectively. The boundaries are presented graphically in Figures 10 and 11 for the two primary outcome measures.

Table 15. CS #2003: Two-sided O’Brien-Fleming Boundaries for Rejection (α) and Acceptance (β) – MCS/VR-36

Interim Look (Stage)	No. of Randomized Participants	Std. z (Rejection)		Std. z (Acceptance)		Type-I error
		Lower	Upper	Lower	Upper	
1	80	-3.12376	3.12376	-0.88945	0.88945	0.00089
2	160	-2.20883	2.20883	-2.20883	2.20883	0.01250

Figure 10. CS #2003 Combined Boundary Plot for MCS/VR-36

[figure not shown]
[figure not shown]

Table 16. CS #2003: Two-sided O’Brien-Fleming Boundaries for Rejection (α) and Acceptance (β) – SCI-QOL Physical Medical Health (PMH) domain

Interim Look (Stage)	No. of Randomized Participants	Std. z (Rejection)		Std. z (Acceptance)		Type-I error
		Lower	Upper	Lower	Upper	
1	80	-3.16956	3.16956	-0.40071	0.40071	0.00076
2	160	-2.24122	2.24122	-2.24122	2.24122	0.01250

Figure 11. CS #2003 Combined Boundary Plot for SCI-QOL Physical Medical Health (PMH) Domain

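### The 0.025 level offered as the adjustment for multiple outcomes controls 5% over the two primaries only; total body fat mass is a third, ungated test at 0.025, taking the nominal error over all three to about 7%.

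*Combined protocol and SAP*

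**What the plan says.** Section XIII.E sets the levels: "All statistical tests will be 2-sided", and "The two primary and major secondary outcome measures will be tested at a 0.025 level of significance". All other secondary outcomes are tested at 0.01.

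Section XIII.B gives the reason for the level: "to adjust for multiple outcome measures, a significance level of 0.025 was used in the sample size calculations for the co-primaries". The same sentence extends 0.025 to total body fat mass, which has its own column in Table 7 (35% against 10%, 85% power).

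Section XIII.F compares the success proportions for each of the three outcomes by a chi-square analysis and adds: "These will constitute the primary and major secondary efficacy analyses". It gives no testing order and does not say whether a continuity correction is used.

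Section XI.J describes stopping-rule methods based on "multiple looks at the primary outcome measures for the review committees while keeping the overall type-I error rate maintained at 5" per cent. This is the only overall error rate in the documents.

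Section XIII.I proposes one interim look at the primary outcomes, with O'Brien-Fleming boundaries for MCS/VR-36 (Table 15) and SCI-QOL (Table 16). It says of the DMC that "it will be necessary for them to see the analysis of the primary and major secondary outcome measures every time" they receive a report and the measures can be calculated. No boundary is given for fat mass.

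**The concern.** The plan offers one adjustment for multiplicity, and it is sized for two tests while three outcomes receive it. Fat mass is more than a descriptive secondary. It has its own hypothesis and power calculation, section II sets it apart from the secondaries called exploratory, and section XVII.B puts it in the primary manuscript.

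As written, a fat mass p-value of 0.02 counts as significant even if both primaries fail. A positive claim could then rest on the one outcome that the 5% does not cover. The plan does not say whether that is intended.

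**Working it through.** **Inputs.** Two-sided 0.025 for each of three outcomes (XIII.E). Control rate 10%; intervention rates 33.3%, 42% and 35%; powers 80%, 95% and 85%; 15% attrition; 80 per group (XIII.B and Table 7). The documents give no correlations between outcomes, so those below are assumptions.

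**1. The plan's own figures reproduce.** The continuity-corrected two-proportion formula at two-sided 0.025 gives 67, 60 and 66 per group. Dividing by 0.85 gives 79, 71 and 78. Both rows match Table 7. Tables 15 and 16, with binding acceptance boundaries and the look at half the information, give one-sided 0.0125 for each primary, which is two-sided 0.025. The two primaries sum to 0.025 + 0.025 = 0.05.

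**2. Three tests, nominal.**
- Upper bound: 3 × 0.025 = 7.5%.
- Independent: 1 − 0.975³ = 7.3%.
- Assumed common correlation between the test statistics (simulation): 7.2% at 0.2, 6.8% at 0.4, 6.5% at 0.5, 5.7% at 0.7.

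Under independence the primaries alone give 1 − 0.975² = 4.9%. The difference, 0.975² × 0.025 = 2.4%, is the chance that fat mass alone is falsely significant.

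**3. Three tests, exact.** Full enumeration with 80 per group and a 10% success rate in both arms:

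| Chi-square version | One test | Three independent tests |
|---|---|---|
| Uncorrected | 2.2% | 6.4% |
| Continuity-corrected | 1.2% | 3.5% |

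At a success rate of 15% to 20% in both arms, the uncorrected three-test figure is 7.1% to 7.3%; the corrected one stays below 5%. Table 7 names the corrected test, for sample size only.

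**4. Error under a gate.** Rule: test fat mass only if a primary is rejected at 0.025, using 0.025 after one rejection and 0.05 after two.
- Neither primary has an effect: any false claim needs a primary rejection first, so the error is at most 0.05.
- One primary has an effect: either the other is falsely rejected (at most 0.025), or it is not and fat mass is falsely rejected at 0.025. The sum is at most 0.05.
- Both have an effect: fat mass is tested at no more than 0.05.

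The bound is 5% in every case, whatever the correlation.

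**5. Fat mass power under the gate** (Table 7 powers, independence, single final analysis).
- Both primaries significant: 0.80 × 0.95 = 0.76.
- Exactly one: 0.80 × 0.05 + 0.20 × 0.95 = 0.23.
- Neither: 0.20 × 0.05 = 0.01.
- Power of 85% at 0.025 implies a mean z of 2.241 + 1.036 = 3.278. At 0.05, power is Φ(3.278 − 1.960) = 0.906.
- Overall: 0.76 × 0.906 + 0.23 × 0.85 = 0.88.

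At an assumed correlation of 0.4, simulation gives 87%. The plan states 85%.

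**The case against.** The best defence is that fat mass is always called a secondary outcome. Adding a secondary test does not raise the error over the primaries, and whether a secondary belongs in the controlled family is a design choice. That stands as far as it goes: no primary claim, sample size or printed boundary is wrong. It does not explain why XIII.B describes the fat mass level as an adjustment for multiple outcomes, or what that adjustment is meant to control.

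A second objection is that 7% is nominal. This also stands. If the final test is the continuity-corrected one, the error over three independent tests at a 10% rate is 3.5%. But XIII.F does not commit to that test, and error control should not rest on an unstated correction.

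Three stronger readings are tempting, and the documents do not support them.
- *The plan promises 5% over all three tests and breaks the promise.* The 5% in XI.J is tied to looks at the primary outcomes, and the two primaries at 0.025 each meet it.
- *The plan declares fat mass confirmatory.* It never uses that word. Its treatment of fat mass makes the inference reasonable, but it remains an inference.
- *The missing interim boundary causes the 7%.* The 7.3% is a single-look figure. XIII.I limits the interim look to the primaries, and no section lets fat mass be declared significant at both looks. If fat mass is tested once, at whichever analysis ends the trial, and is independent of the primaries, its error stays at 0.025.

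**Conclusion.** The concern holds as a gap in the specification. The 0.025 level controls 5% over the two primaries only. Adding fat mass without a gate brings the nominal error over the three powered outcomes to 7.3% under independence, and to no more than 7.5% under any dependence. Positive correlation lowers it, to 6.8% at an assumed 0.4. The exact error at a 10% rate is 6.4% or 3.5%, depending on the unstated correction.

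The practical harm is confined to a fat mass claim made when both primaries have failed. Severity: should-fix.

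Separately, and adding nothing to the 7%, Tables 15 and 16 leave open how fat mass is judged if a primary stops the trial at the interim look.

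**What to change.** In XIII.E, state that total body fat mass is tested only if at least one primary is significant at its own level: at 0.025 if one primary is rejected and at 0.05 if both are. If neither is, report the estimate and interval with no claim of significance. In XIII.F, say whether the chi-square is continuity-corrected. In XIII.I, state the boundary for fat mass if the trial stops at the interim look.

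The cost is a short paragraph of SAP text, to be settled before unblinding. The sample size stays at 160 and fat mass power does not fall on the Table 7 assumptions. The one loss is a fat mass claim when both primaries fail.

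A three-way split at 0.05/3 would keep that claim available, but needs 73, 65 and 72 per group. Divided by 0.85, these become 86, 77 and 85, so 172 in total. If 160 were kept, continuity-corrected MCS power at 68 completers per group would fall from 81% to 77%. The gate is the cheaper choice.

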A major secondary objective of the study is to demonstrate that participants who use the exoskeleton in addition to SOC (EAW+SOC) will have at least a 1.0 kg loss in total body fat mass by the end of the four-month intervention compared to those who receive SOC only. Other secondary objectives are to demonstrate that participants in the EAW+SOC group will have greater net improvements than participants in the SOC only group in the following outcomes: 1) Global Impression of Change (participant- and companion-rated), 2) disturbed sleep as measured by the T-score of the Patient Reported Outcomes Measurement Information System (PROMIS) Sleep Disturbance, 3) self-reported methods and measures of bowel function, 4) sum T scores of the SCI Functional Index (SCI-FI) physical function short forms, 5) sum T scores of the SCI-QOL Emotional domain, 6) sum T scores of the SCI-QOL Social Participation domain, 7) lipid profile for high density lipoprotein cholesterol (HDL-c), low density lipoprotein cholesterol (LDL-c), triglycerides (TG), and total cholesterol (TC), and 8) fasting plasma glucose (FPG) and insulin (FPI) levels for calculation of Homeostasis Model of Assessment-Insulin Resistance (HOMA-IR).

B. Sample Size

Using preliminary data generated from the Exoskeletal-assisted Walking Program at the James J. Peters VA Medical Center, three separate power calculations were performed, one for each of the primary outcome measures, the MCS/VR-36 and the sum t-score of the SCI-QOL bladder, bowel and pain item banks, and one for the major secondary measure, total body fat mass. The sample

size estimates are based on the preliminary data from these three outcome measures as a proportion of participants who achieved a clinically significant change score (MCS/VR-36 and Total Body Fat Mass) or a clinically significant percent change (SCI-QOL PMH).

Sample size/power calculation for the Primary Outcome (1) MCS/VR-36: A minimally important difference for the MCS/VR-36 is 4.0. It is hypothesized that 33% of the Intervention group and 10% of the Control group will achieve a 4.0 or greater change on the MCS/VR-36 (Table 7).

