presenting baseline participant characteristics and outcome measures by treatment group. Differences between treatment groups on participant characteristics may indicate a need to use any significantly different characteristics as covariates for the outcome measures. Formal testing of the differences between treatment groups will be done at the study’s conclusion. Analyses of variance techniques will be used to test characteristics that are continuous in nature, while chi-square techniques will be used for the discrete variable characteristics. The analyses of the primary and major secondary outcome measures are described above in section F. The results of these analyses will be provided in table format and will include the p-value from the chi-square analysis. Table 13 indicates how the MCS/VR-36 outcome measure will be displayed. Analyses of the SCI-QOL Physical Medical Health domain (three item banks for bladder management difficulties, bowel management difficulties and pain interference) and total body fat mass outcome measures will be presented in a similar fashion.

Table 13. CS #2003 Primary Outcome Measure: Mental Component Summary (MCS) of the VR-36

≥ 4-point improvement in MCS/VR-36 from baseline to end of 4-month intervention	SOC		EAW + SOC		Total		p-value
	n	%	n	%	n	%	
Success							
Failure							
Total							

Secondary outcome measures and analyses (as outlined in section G above) will also be provided in tabular format. These tables will present statistics for the outcome variables at all the time points at which the outcome measures are assessed: baseline, after the training/orientation Phase, two months into the 4-month intervention phase, and then again at the end of the intervention phase. Again using the MCS/VR-36 as an example, Table 14 indicates how these data may be presented. The p-values from the comparison of the difference scores (difference from baseline to the end of each time point) and from the mixed models analyses, as appropriate, will also be presented in these tables.

Table 14. CS #2003: VR-36 Mental Component Summary (MCS) Scores

Time Point	SOC				EAW + SOC			
	N	Mean	Std. Dev.	Median	N	Mean	Std. Dev.	Median
Baseline								
Post-Training/Orientation								
Two Months into Intervention Phase								
Post-Intervention Phase								

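### The plan gives two critical values for the final MCS/VR-36 test, |z| 2.2414 in XIII.E and 2.20883 in Table 15, and does not say which applies or whether the interim acceptance bound is binding

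*Combined protocol and SAP*

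**What the plan says.** - **Level (XIII.E).** "All statistical tests will be 2-sided", and "The two primary and major secondary outcome measures will be tested at a 0.025 level of significance". Neither sentence refers to an interim look or calls 0.025 an overall level.
- **Origin of 0.025 (XIII.B).** "to adjust for multiple outcome measures, a significance level of 0.025 was used in the sample size calculations for the co-primaries", and also for total body fat mass. XI.J gives the overall target for repeated looks: "keeping the overall type-I error rate maintained at 5" per cent.
- **Final test (XIII.F).** A chi-square comparison of success proportions, with no adjusted critical value.
- **Interim look (XIII.I).** One look is proposed when 80 participants (50%) have completed. The sentence proposing it gives the choice as continuing or stopping for early efficacy. O'Brien-Fleming rejection and acceptance boundaries are suggested, and the "Type-I error rates for the two looks are given in Tables 15 and 16 for the MCS/VR-36 and SCI-QOL/PMH outcomes, respectively".
- **Table 15 (MCS/VR-36).** Stage 1: reject at |z| 3.12376, accept at 0.88945, Type-I error 0.00089. Stage 2: |z| 2.20883, Type-I error 0.01250.
- **Table 16 (SCI-QOL).** Stage 1: reject at 3.16956, accept at 0.40071, Type-I error 0.00076. Stage 2: |z| 2.24122, Type-I error 0.01250. Both tables are titled two-sided.
- **What the DMC sees (XIII.I, Table 13).** "The results of these analyses will be provided in table format and will include the p-value from the chi-square analysis".
- **Who decides (XI.J).** The DMC makes the final choice of stopping rule.

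**The concern.** Applying XIII.E and XIII.F as written means comparing the final MCS/VR-36 chi-square with |z| 2.2414. Applying Table 15 means comparing it with 2.20883. Nothing ranks one above the other, so a result between them has no agreed reading on a primary outcome.

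The Table 15 value is the more lenient, which is unusual for a final look after an interim. It comes from error recovered by stopping at the interim when |z| is small. If the trial may continue after such a result, the leniency is not paid for and the overall error exceeds 0.025. The sentence proposing the look mentions only efficacy stopping, so this needs settling before outcome data are reviewed.

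There is also a labelling problem. The DMC receives two-sided chi-square p-values, but the only probabilities printed beside the boundaries are one-sided and are not labelled so.

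**Working it through.** **Inputs.** Level 0.025 two-sided (XIII.E); boundaries from Tables 15 and 16; look at half the information (80 of 160, XIII.I). MCS/VR-36 design: "33% of the Intervention group and 10% of the Control group will achieve a 4.0 or greater change on the MCS/VR-36" (0.333 in Table 7), "79 per group (80% power) for the MCS/VR-36 group" including attrition. The look statistics Z1 and Z2 are taken as bivariate normal with correlation √0.5.

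**1. Design level.** The continuity-corrected sample size at two-sided 0.025 for 0.100 v 0.333 with 80% power is 67 per group, and 67/0.85 = 78.8, so 79. This reproduces Table 7 and confirms a design level of 0.025 two-sided.

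**2. Nominal p-values of the printed boundaries, p = 2 × (1 − Φ(z)).**

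| Boundary | One tail | Two-sided p |
|---|---|---|
| MCS stage 1, 3.12376 | 0.00089 | 0.00179 |
| MCS stage 2, 2.20883 | 0.01359 | 0.0272 |
| SCI-QOL stage 1, 3.16956 | 0.00076 | 0.00153 |
| SCI-QOL stage 2, 2.24122 | 0.01251 | 0.0250 |

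A plain two-sided 0.025 test has |z| = 2.2414. The stage-1 Type-I errors in both tables equal the single-tail areas.

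**3. Reproducing Table 15 with acceptance binding.** Error per tail = P(Z1 > 3.12376) + P(0.88945 < |Z1| < 3.12376, Z2 > 2.20883) = 0.00089 + 0.01161 = 0.01250. Two-sided: 2 × 0.01250 = 0.0250. At 80% power the drift is 3.1598, and the stage-1 acceptance bound is 3.1598 × √0.5 − (3.1598 − 2.20883) × √2 = 0.889, as printed. Table 16 reproduces in the same way: 0.0250 two-sided, with acceptance bound 0.4007 at 95% power. The printed boundaries are therefore correct for a binding design, and 0.01250 is the cumulative error per tail.

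The MCS/VR-36 final boundary falls below 2.2414 because the acceptance bound stops 62.6% of null trials at the look (P(|Z1| < 0.88945) = 0.626).

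**4. Same boundaries, acceptance not binding.** Error per tail = P(Z1 > 3.12376) + P(|Z1| < 3.12376, Z2 > 2.20883) = 0.00089 + 0.01305 = 0.01395 (from unrounded terms). Two-sided: 0.0279. Table 16 gives 0.0256. The sum is 0.0279 + 0.0256 = 0.0535, an upper bound on the error over the two primaries, against 0.05.

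**5. Overall two-sided error for each final cut-off, using the printed stage-1 rejection bounds.**

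| Final cut-off | Binding | Not binding |
|---|---|---|
| MCS, 2.20883 | 0.0250 | 0.0279 |
| MCS, 2.2414 | 0.0232 | 0.0257 |
| SCI-QOL, 2.24122 | 0.0250 | 0.0256 |

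**6. Efficacy-only O'Brien-Fleming at overall 0.025.** Solve 2 × [P(Z1 > c√2) + P(|Z1| < c√2, Z2 > c)] = 0.025. This gives c = 2.2505 (two-sided p 0.0244) and an interim bound of 2.2505 × √2 = 3.183, for both primaries.

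**7. A result in the gap.** 7/80 v 17/80, uncorrected Pearson: difference 0.125, pooled proportion 0.15, standard error √(0.15 × 0.85 × 2/80) = 0.05646, z = 2.214, p = 0.0268. This is not significant under XIII.E and significant under Table 15.

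**8. How often the gap matters.** Exact binomial enumeration at 80 per arm (uncorrected Pearson, final look alone) puts |z| between 2.20883 and 2.2414 with probability 0.3% at 10% v 33.3%, 0.4% at 10% v 10%, and about 1.6% at 10% v 20% to 22%.

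**The case against.** The strongest reply is that nothing conflicts. A significance level and a group-sequential critical value are different quantities. Table 15 delivers exactly 0.025 two-sided with acceptance binding, the tables print acceptance bounds, and XI.J and XIII.I both contemplate stopping when differences are too small. On that view 0.025 is naturally the overall level and 2.20883 the cut-off that achieves it. This is probably what was intended, and the arithmetic supports it. But the plan does not state it: XIII.E and XIII.F give a plain test at 0.025, and the sentence proposing the look omits futility stopping.

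The boundaries are also only suggested, and the DMC meets before start-up to set its procedures. That is true, and the documents give nobody the right to choose a threshold after seeing results. Even so, XIII.E has no wording for what the final test becomes once the DMC adopts a rule.

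The gap is small, as step 8 shows. The 7/80 v 17/80 example also depends on an uncorrected chi-square. With the continuity correction assumed in Table 7, z = (0.125 − 0.0125)/0.05646 = 1.99 and p = 0.046, negative under either cut-off. XIII.F does not say which form is used.

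A reader might infer a third threshold, 0.0125, from the Type-I error column. The documents do not support that. A two-sided p cut-off of 0.0125 needs |z| of about 2.50, while the same row prints 2.20883, and the stage-1 entries are visibly single-tail areas. The column is poorly labelled and sets no competing rule.

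**Conclusion.** The point holds as an unresolved cut-off for one primary outcome. XIII.E and Table 15 give different final critical values for MCS/VR-36. They reconcile only if 0.025 is the overall level and acceptance is binding, and the plan states neither. The consequences are limited: a final p between 0.0250 and 0.0272 can be called either way, and without binding acceptance the overall two-sided error is 0.0279 for MCS/VR-36 and 0.0256 for SCI-QOL, against 0.025 each. For SCI-QOL the printed final boundary in effect equals 0.025, so only the binding question and the column label remain.

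It would go too far to say that the plan sets three conflicting significance levels or that Table 15 is miscalculated: its boundaries reproduce, and 0.01250 per tail is 0.025 two-sided. The figures assume normal test statistics, a look at exactly half the information, and the printed boundaries being adopted. The matter deserves correction because it is a primary decision threshold and the repair is cheap.

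**What to change.** 1. **XIII.E.** State that two-sided 0.025 is the overall level for each primary across the interim and final looks; that the final test uses the stage-2 boundary of the design the DMC adopts before any outcome data are reviewed; and that a flat 0.025 applies only if no interim look is adopted.
2. **XIII.I, binding status.** State one of two options.
   - *Binding:* keep the printed boundaries (final MCS/VR-36 |z| ≥ 2.20883, p ≤ 0.0272; SCI-QOL |z| ≥ 2.24122, p ≤ 0.0250) and amend the sentence proposing the look to say that it can also stop for futility.
   - *Not binding:* replace them with efficacy-only O'Brien-Fleming boundaries at overall 0.025 (final |z| about 2.250, two-sided p about 0.0244, for both primaries). Fixing 2.20883 without the binding condition would leave the error at 0.0279.
3. **Tables 15 and 16.** Relabel the Type-I error column as cumulative one-sided error (per tail), and add the two-sided nominal p for each boundary, for comparison with the chi-square p-value. As printed these are 0.00179 and 0.0272 for MCS/VR-36, and 0.00153 and 0.0250 for SCI-QOL.

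**Cost.** A few sentences and two table edits, with no change to participants or data. The binding option obliges the trial to stop if the acceptance bound is met. The non-binding option makes the final threshold slightly stricter.
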